## 5.4 **Protocol Schedule**

The study comprises five stages: Pre-study, Baseline, Verification, Treatment, and Post-Study.

- **Pre-Study** –The subjects initiate pre-study activity, which includes completion of the I-QoL Questionnaire, the Pre-study Incontinence History and Usability Questionnaire, and the 24-hour pad weight test. The subject mails the pre-study materials back to Elidah. There is no difference in requirements between the two study arms.
- **Baseline** –Concurrently, the subjects maintain the Daily Log for 7 days to establish a baseline of the episodes/day and pads/day measures. No treatment is administered during this period. After 7 days the subjects submit the data to Elidah (electronically or hardcopy). Subjects are instructed that they should not perform baseline activity during menses or if they are ill. Note that it is acceptable to complete or return the pre-study materials throughout this 7 day baseline period. There is no difference in requirements between the two study arms.
- **Verification** If the 7 day baseline shows that the subject does not qualify based on urinary stress incontinence episodes, then the subject will be disqualified and the device will not be sent.
- Treatment Subjects will self-administer treatment with the Elitone device or a sham device according to their group assignment. The prescribed number of treatments starts at 5x/week and is reduced at points throughout the 12-week study duration. See Section 6 and Table 5-1 for a detailed description of the device and the treatment schedule. If subjects are ill or in menses during the twelfth study week they are instructed to extend treatment for at least 5 days after menses and/or they are in good health.
- Post-Study Upon completion of treatment subjects complete the post-study requirements, which include the I-QoL questionnaire, a 24-hour pad weight test, and a post-study usability

questionnaire. Subjects are requested to complete the requirements and return the study materials to Elidah within 3 days of completing treatment. There is no difference in post-study requirements between the two study arms.

 
Data used in primary and secondary endpoint analysis
 
Used to establish compliance.
 
	I-QoL Questionnaire	24-Hour Pad Weight Test	Pre-Study Usability Questionnaire	Number of Self- administered Treatment	Daily Log	Post-Study Usability Questionnaire	Adverse Events			
Pre-Study Data	•	•	•							
Baseline (Week 0)				0	•					
Treatment (Week 1)				5	0		•			
Treatment (Week 2)				5	0		•			
Treatment (Week 3)				5	0		•			
Treatment (Week 4)				5	0		٠			
Treatment (Week 5)				5	0		٠			
Treatment (Week 6)				5	0		•			
Treatment (Week 7)				3	0		٠			
Treatment (Week 8)				3	0		•			
Treatment (Week 9)				3	0		•			
Treatment (Week 10)				1	0		٠			
Treatment (Week 11)				1	0		•			
Treatment (Week 12)				1	•		٠			
Treatment (Week 13)*				1	•		٠			
Post-Study Data	•	●				●	•			
* As needed. See description of treatment above.										

## Table 5-1: Schedule of Study Activities/Requirements for Active and Control Groups.

### 5.5 Adherence Assessment

Adherence to the study regimen for the active group requires completion of  $\geq 60\%$  (18) of the treatment sessions prescribed during the first 6 weeks, as determined from review of each subject's Daily Log.

Elidah anticipates that subjects' willingness to continue with a frequent treatment schedule may diminish with time for reasons including:

- The subject achieves meaningful clinical improvement or complete elimination of incontinence symptoms during the early weeks of the study
- The subject believes she is in the control group
- The subject is not achieving clinical improvement and become discouraged with the likelihood of future improvement.

• Change in the subject's schedule and/or lifestyle

Accordingly, the prescribed treatment frequency over the latter half of the study is reduced (see Table 5-1). Correspondingly the minimum number of treatment sessions required for adherence is reduced to 1x/week for weeks 7-9 (33%) and 0x/week for weeks 10-12 (0%).

Further, subjects must complete the Pre-study, Baseline and Post-Study requirements to be considered compliant. If a subject does not adhere to the study requirements they will be asked to provide a reason, which will be documented in the Case Report Form (TR-1131-FORM-10). During data analysis, this information will be reviewed by the Data Safety and Monitoring Board to determine if/how the data should be adjudicated (see 10.5).

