### 9.5 Data Analyses

Analysis of the **primary efficacy endpoint** will proceed as follows. Each adherent subject's Daily Log will be used to determine the average number of SUI episodes per day for the baseline and  $12^{th}$  weeks (see 5.5 regarding subject adherence). To accommodate the likelihood that some subjects will omit log data, the "weeks" referred to in the baseline and 12th week assessments refer to the first and last 5 entries in the Daily Log. The percent reduction in SUI episodes is then calculated by subtracting the final week average from the baseline average, dividing the difference by the baseline average, and multiplying by 100. Subjects with a percent reduction of  $\geq$ 50% are considered responders. The number of responders from each group is then compared using a one-tailed Fisher's exact test for groups of unequal size, and p $\leq$ 0.025. For example, if 24 of 40 subjects (60%) from the active group responded and 5 of 20 (25%) from the control group responded, the active treatment would be considered effective (p=0.01).

SUI episodes per day data can additionally be characterized simply in terms of percent reduction (independent of whether it reaches a 50% level of clinical significance) and the treatment groups analyzed using a 2 sample t-test with unequal group sizes. This approach is commonly reported in the literature. This value may additionally be reported but is not intended for use in determining whether the study met its endpoint. This use of a secondary analysis method on a single endpoint after success of the primary analysis method is generally understood to not inflate the Type 1 error rate, so no multiplicity adjustments are necessary.

Also note that confidence intervals and associated effect size calculations may also be made on the same data, but no multiplicity adjustments are warranted. Similarly, the data may be additionally analyzed using intent-to-treat criteria instead of with per-protocol criteria as defined in 5.5.

Regarding **secondary outcome measures**, three tests are prospectively defined with the intent of using the results to support future product labeling and marketing. The Hochberg procedure

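### The only confirmatory test uses an adherence-defined set chosen after randomisation, with optional intent-to-treat and no stated rule or blinding for adjudication, so the 2.5% type I error is not assured

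*Combined protocol and SAP*

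**What the plan says.** Section 9.5 builds the primary endpoint this way: "Each adherent subject's Daily Log will be used to determine the average number of SUI episodes per day". Subjects with a reduction of at least 50% are responders, and the arms are compared by a one-tailed Fisher's exact test at 0.025. Baseline and final weeks "refer to the first and last 5 entries in the Daily Log". On the alternative population it says only that "the data may be additionally analyzed using intent-to-treat criteria instead of with per-protocol criteria as defined in 5.5"; no intent-to-treat set is defined.

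Section 5.5 supplies the adherence criteria:
- Weeks 1–6: "Adherence to the study regimen for the active group requires completion of" at least 60% (18) of the prescribed sessions.
- Weeks 7–9: once a week. Weeks 10–12: none required. Neither names an arm.
- Both arms: "subjects must complete the Pre-study, Baseline and Post-Study requirements to be considered compliant". Under 5.4 the pre- and post-study items are questionnaires and pad tests.
- Reasons for non-adherence go to the Data Safety and Monitoring Board, which decides during data analysis whether and how the data are adjudicated. No criteria are given. Section 10.5, to which 5.5 refers, gives the board's minimum membership, including the Clinical Director, but no rule.

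Table 5-1 is captioned "Schedule of Study Activities/Requirements for Active and Control Groups" and sets one schedule for both. Sections 5.7 and 9.3 blind the staff who do subject-level calculations; blinding ends at group analysis.

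**The concern.** Randomisation protects a comparison only if the people compared are the people randomised, or a subset chosen without regard to arm and outcome together. Here the subset depends on behaviour during treatment. Section 5.5 expects use to fall for reasons tied to outcome and perceived assignment, among them "The subject believes she is in the control group" and "The subject is not achieving clinical improvement and become discouraged with the likelihood of future improvement". It also lists early improvement. Section 6.6 gives the sham a different waveform, lower current and a shorter session, so these reasons need not act equally in the two arms. Even one shared session rule could then remove different kinds of women from each arm.

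The adjudication step adds discretion at the point where it matters most. If membership can depend on outcome differently by arm, a significant p-value does not by itself establish efficacy, and a non-significant one may understate it.

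**Working it through.** **The plan's own figures.** Section 9.1 gives treatment groups of 31, 16 and 12 (one-sided alpha 0.025, 80% power, 2:1). With n = (1.960 + 0.842)² × [pT(1−pT) + 2pC(1−pC)] / (pT−pC)², the pairs 48/13, 62/13 and 71/15% give 30.5, 15.1 and 11.5, which round up to 31, 16 and 12. The worked example, 24/40 v 5/20, gives a one-sided Fisher p = 0.0105 (stated 0.01). Both reproduce.

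**Inputs for selection.**
- From the plan: the test, the 0.025 limit, 2:1 allocation, control rates of 13% and 15% (sizing, 9.1) and 25% (example, 9.5), and 70–80 enrolled for 60 (loss of 10/70 = 14% to 20/80 = 25%).
- Assumed: 50 active and 25 control randomised, a 35% rate as an upper case, and all filters below. The documents give no adherence or dropout rate by arm.

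**Method.** With no true effect, both arms share responder rate p. If a filter removes share fN of non-responders and fR of responders, the retained share is r = p(1−fR) + (1−p)(1−fN), and the responder rate among those retained is p* = p(1−fR)/r. Example: p = 0.25 with filter 30/10 gives r = 0.225 + 0.525 = 0.75 and p* = 0.225/0.75 = 0.30. Type I error is the exact sum, over binomial numbers retained and binomial responders in each arm, of the probability that the one-sided Fisher p is at most 0.025.

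| Filter (non-responders/responders removed, %) | p=13% | 15% | 25% | 35% |
|---|---|---|---|---|
| None | 0.007 | 0.008 | 0.012 | 0.014 |
| 30/10 in both arms | 0.007 | 0.008 | 0.012 | 0.013 |
| Active 30/10, control kept | 0.021 | 0.024 | 0.034 | 0.041 |
| Active 30/10, control 10/10 | 0.018 | 0.021 | 0.032 | 0.039 |
| Active 20/10, control kept | 0.013 | 0.015 | 0.020 | 0.023 |
| Active 20/10, control 10/20 | 0.014 | 0.018 | 0.029 | 0.035 |
| Active 10/30, control kept | 0.003 | 0.003 | 0.004 | 0.004 |

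The driver is selection that differs between arms. Fisher's test is conservative at this size and absorbs the milder filters. None of those in the table passes 0.025 at 13–15%. That is not a general bound: removing 30% of active non-responders and nobody else gives 0.030 at 13% and 0.035 at 15%.

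**The replacement rule, tested the same way.** Analyse all 50/25, count missing as non-response, and let missingness be unrelated to outcome. Each arm's rate becomes p(1−missing share).

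| Missing, active/control | p=13% | 15% | 25% | 35% |
|---|---|---|---|---|
| 20%/20% | 0.005 | 0.007 | 0.010 | 0.013 |
| 15%/25% | 0.008 | 0.011 | 0.019 | 0.029 |
| 10%/30% | 0.012 | 0.017 | 0.034 | 0.056 |

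The rule is safe under equal missingness but not if controls drop out much more. A tipping-point analysis exposes this: 24/50 v 5/25 gives p = 0.0164, but one missing control counted as a responder (6/25) gives p = 0.0384.

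**Power (exact Fisher).** For 48 v 13, 62 v 13, 71 v 15 and 60 v 25%: 73.5/95.5/98.6/64.1% at 40/20 per-protocol, against 69.3/93.4/97.2/59.3% at 50/25 with 20% of each arm counted as failures.

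**The case against.** Four arguments deserve weight.

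1. A reader might infer that the 18-session rule removes active subjects only, leaving controls untouched. The documents do not support this. Table 5-1 covers both groups, 9.5 refers to adherent subjects without naming an arm, and blinded staff reviewing diaries could not apply an active-only threshold. The wording needs a clarification and no more.
2. Judging adherence from a diary is naturally subject-level work, so it is arguably blinded under 5.7 and 9.3. This stands for the session count. It does not reach the board's adjudication, for which no blinding is stated. A reader might also infer that the board will remove controls who report contraction, because 6.6 sends it their forms. No such consequence is stated.
3. Missing a pad test or questionnaire makes a subject non-compliant under 5.5, but exclusion from the primary analysis is not said to be automatic. That stands: it is an ambiguity, and the plan should settle it.
4. A reader might infer that the test is inflated in the device's favour. The documents do not show that. Section 5.5 offers its reasons to justify a lighter later schedule, not to predict who will miss 18 sessions, and they include early improvement, which would work against the device. Every filter here is assumed. The 14–25% allowance is for women who drop out or do not return materials; it is not evidence of outcome-related exclusion that differs by arm.

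What remains is that a superiority claim rests on a post-randomisation set with an open adjudication step, and an optional, undefined intent-to-treat analysis cannot protect it.

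**Conclusion.** The point holds as a failure to assure type I error, not as a demonstration that it is exceeded. The gap in the text is certain: adherent-only primary analysis, undefined intent-to-treat, and adjudication during analysis without a stated rule or blinding. The size is unknown and the direction open. Under the assumed filters at 50/25, type I error runs from about 0.003 (selection against the device) to 0.041 (active 30/10 only, 35% rate). Among the tabulated filters the breaches occur at the 25% rate of the plan's example and at the assumed 35%, not at its 13–15% sizing rates. An identical filter in both arms causes no inflation. The change should be made before any group analysis, including the interim looks in 9.4, because a primary set redefined after unblinding would carry little weight.

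**What to change.** In 9.5:
- Make the primary set all randomised subjects who pass baseline Verification, decided from pre-treatment data blind to arm and analysed as randomised. Assignment happens at return of consent (9.2), before Verification (5.4), so this needs stating.
- Use every usable diary, whatever the session count and whether or not a pad test or questionnaire is missing.
- Set one missing-outcome rule for both arms. Keep a stated tolerance for omitted entries within the final window (week 12, or the week 13 extension when it applies). Do not let entries from before that window serve as the outcome. Count subjects with no usable final-window diary as non-responders.
- Report missingness by arm, with a pre-specified tipping-point analysis that includes missing controls counted as responders. This exposes the effect of unequal dropout but does not restore error control.
- Keep per-protocol as a sensitivity analysis, with membership and adjudication fixed blind to arm before group analysis.

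In 5.5, state that one session rule applies to both arms. In section 8, extend the follow-up effort to the final-window diary days; the post-study activities listed in 5.4 do not include the diary.

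**Cost.** Mostly wording, plus a few diary days from women who stop early. Early improvers who stop logging would count as failures. Power falls by about 1 to 5 percentage points in the four scenarios under the 20% assumption, and for 48 v 13 and 60 v 25 it is below 80% under either approach. Restoring 80% there with 20% counted as failures would take about 64/32 (96 subjects) and 76/38 (114), against the 70–80 planned. The sponsor should restate power for the new set and decide whether to accept the loss or enlarge the trial.

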## 5.6 Concomitant Medications

Concomitant medications are defined as any prescription or over-the-counter medication (including hormonal contraception, vitamins, food supplements, and herbal preparations) taken seven days prior to initiation of pre-study activity through completion of post-study activity. Subjects will be instructed not to take any new concomitant medications unless medically necessary. If the use of a new concomitant medication becomes necessary, the treatment must be recorded in the Case Report Form (TR-1131-FORM-10), including the name of the medication, dosage, route of administration, date, and indication for use.

### 5.7 Blinding

Subjects will be blinded to the assigned treatment group. The individual(s) performing subject level data analysis will be blinded to the treatment arm. Due to the 2:1 assignment ratio blinding, assignment must be revealed during group analysis. See 9.3 for addition discussion of blinding.

## 6. ELITONE DEVICE

### 6.1 Device History

The Elitone device has been evaluated clinically in prior IRB approved study WIRB-20162650, WIRB 20180640. See 9.1 for additional information regarding the outcomes from that study. For the current study, only minor modifications have been implemented with respect to the software, stimulation waveform and treatment regimen.

#### 6.2 Description of Treatment Regimen

The Elitone device delivers electrical current through an electrode component applied to the perineal region, stimulating the pelvic floor muscles and surrounding structures to improve continence. Per the product labeling, stimulation is delivered in continuous on-off cycles, 20 minutes per session, 5 sessions per week for 6-12 weeks. In this study, the treatment frequency is more explicitly defined as detailed in Table 5-1. The design allows for convenient home-use. It comprises two main components: a disposable electrode and a controller.

# CONFIDENTIAL

Figure 6-1: Rendering of Elitone device worn on the female anatomy, under clothing.

## 6.3 Electrode Component

The electrode component is worn against the skin in the perineal region. The conductive regions are positioned such that when stimulated they deliver electrical current proximate the pelvic floor muscles. The base of the electrode is a flexible conductive ink circuit. The patient contacting elements are hydrogel and foam. Two snap connections are present on the surface facing away from the patient, which provide a connection point to a cable and the Controller component. Each electrode is provided on a removable release liner that aids in maintaining the adhesiveness and hydration of the hydrogel during use and reuse. All materials used in the electrode have histories of use in similar electrodes.

Figure 6-2: LEFT - Patient contacting side of electrode component, including conductive regions (blue) seen through the removable release liner. RIGHT - Opposite side of electrode component, including snaps for cable connection.

The electrodes are packaged in quantities of five in a resealable pouch. They are identified as part number EE-1002, and the packaging includes a lot number and Use By date. Each subject is provided with sufficient electrodes to allow use of a new electrode every other treatment session.

## 6.4 Controller Component and Accessories

The Controller component is used to supply the stimulating current. It comprises a circuit board, rechargeable battery, and user interface, all housed within a plastic housing approximately 2" x 1.5" x 0.5". The device is programmed to deliver the stimulation waveform described in 6.5. The

device outputs 0-50mA (RMS) and 0-100V into a 500 $\Omega$  load, which is similar to numerous commercially available electrical muscle stimulation devices and meets electrical safety standards for EMS devices (see 7.1). The output intensity is controlled by the user through a pair of increment and decrement buttons. The device can deliver at least two twenty-minute treatments on a battery charge. Recharging of the 3.7V lithium polymer battery is achieved via conventional micro-USB to USB cable. The battery includes integrated overload protection circuitry. In addition to the increment/decrement buttons, which also serve to turn on and pause/stop the device, the user interface includes a series of colored LEDs that indicate power state, and treatment intensity.

Each controller has a label that specifies the part number (EC-1003) and lot number. For the subject study, an additional label is applied that identifies the unit as "for investigational use only" and provides a unit reference number. Each subject is provided with a single controller. Accompanying the controller are additional components required for operation including the patient cable, USB charging cable, user manual, belt clip and product packaging. Note that portions of the user manual (TR-1131-FORM-12) have been modified to support blinding of the subject to her treatment group.

Figure 6-3: LEFT – Elitone controller. RIGHT – Controller and all accessories, including the User Manual, Patient Cable, Charging Cable, Belt-Clip (attached to Controller) and device packaging.

## 6.5 Stimulation Waveform

The Controller outputs a two part stimulation signal with a base of 2000 Hz and modulated at 50 Hz and 10 Hz. The first part operates at 50 Hz for 4 seconds and is intended to affect stress urinary incontinence symptoms. The second part operates at 10 Hz for 2 seconds and is intended to affect urge urinary incontinence. After the stimulation is delivered the output goes to zero for 6 seconds. This on/off cycling of the stimulation output continues for the duration of the treatment. Intensity is set by the user, who is instructed to operate the device at a level that is maximally tolerated for the duration of treatment. Variations on this stimulation signal are permissible and achievable due to circuit design, which utilizes a programmable microcontroller.

## 6.6 Control/Sham Device

Subjects in the control group will receive a sham device that is identical to the Elitone device except for the firmware parameters that define the stimulation waveform and therapy session.

The stimulation waveform for the sham occurs as a higher frequency and lower current, and the treatment session duration is also reduced. These parameters and intended to elicit a surface sensation, but not to induce contraction of the pelvic floor muscles or to have a therapeutic benefit.

As part of the post-study surveys subjects will be asked to describe any sensation they felt, whether they felt any contraction of the pelvic floor, and whether they believe they received a treatment or a sham device. The Data Safety and Monitoring Board will review the Case Repot Forms of any subjects in the control group who report contraction of the pelvic floor muscles (see 10.5)

## 6.7 Regulatory Status

The Elitone device is presently under review by the FDA as part of the De Novo process. This study is in part designed to support a request for additional information made by the FDA.

#### 6.8 Procurement

The electrodes, controller and all accessories are designed and manufactured by Elidah, which operates in accordance with its ISO 13485 certification for the design and manufacture of medical devices. Where applicable the product will be provided to the subjects with suitable remaining shelf life. All subjects will receive new electrodes. Subjects may be provided previously used controllers or accessories that have been inspected and confirmed to meet performance requirements.

